### **7.2.5. Statistical Analyses / Methods**

Asthma exacerbations will be summarized for the periods: Weeks 1-52, Weeks 1-24, and Weeks 25-52 (see Section 11.6.3), including the following details of the event:

- Number of participants contributing to the reporting period
- Duration of time in reporting period (days)
- Number and percent of participants with moderate / severe exacerbations (0, 1, 2, >2)
- Number of moderate / severe exacerbations
  - Number and percent of exacerbations that required hospitalization, emergency room visit, or the use of systemic corticosteroids.
  - Outcome and duration (days) of moderate/severe exacerbations
- Number and percent of participants with severe exacerbations
  - Require hospitalization
  - Require visit to emergency room
  - Require the use of systemic corticosteroid
- Number and percent of participants with moderate exacerbations
  - Number with deterioration in asthma symptoms, deterioration in lung function, increased rescue bronchodilator use (and all possible combinations of the three).
  - Number who took medication

Summaries for weeks 1-52 will also be provided by gender, age, race, region, pre-study ICS dosage at screening, BMI and CV History/Risk Factor at Screening.

The exacerbation rate will be analyzed using a generalized linear model, assuming the number of exacerbations has a negative binomial probability distribution and that its mean is related to covariate factors with a 'log link' function. The logarithm of time (year) on study will be used as an offset variable. Missing data due to early withdrawal from the study will not be imputed.

The exacerbation rate over the first 24 weeks of the study will also be analyzed in the same manner.

Supportive analysis for the pooled FF doses, based on 'de jure' type estimand will be performed, including all on-treatment moderate/severe exacerbation data collected during double-blind treatment period.

Sensitivity analysis will be performed for the key secondary efficacy endpoint based on the 'de facto' type estimand, excluding all randomized participants enrolled at Site No. PPD [REDACTED] and Site No. PPD [REDACTED] as a result of study non-compliance based on the GSK issue-investigation report, and the standard GSK monitoring and auditing practices. Additionally, subjects randomized at sites PPD [REDACTED] and PPD [REDACTED] will be excluded due to a lack of confidence in the data received.

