The 'de facto' type estimand analysis for the key secondary endpoint includes all moderate/severe asthma exacerbations following discontinuation of randomized treatment for participants who remain in the study and assumes that any remaining missing data due to early withdrawal from study prior to the planned end of study visit is Missing at Random (MAR). To examine the sensitivity of the analysis result to departures from this assumption, further sensitivity analyses will be performed using alternative assumptions analogous to those used for the primary endpoint. For each proposed imputation method, the sensitivity analysis will include both observed (on and post-treatment) and imputed asthma exacerbation events. The following different algorithms are proposed to impute the post-treatment missing data.

These analyses will be performed for weeks 1-52 only.

For each approach, exacerbations in the unobserved period will be imputed only up to the participant's planned end of study visit date determined by participant's randomization date (see Section 11.3.2).

- Tipping Point:

This method will explore the potential effect of missing data on the reliability of the results by using different assumptions regarding the moderate/severe asthma exacerbation rate in participants who withdraw from study early. Participants who withdrew from the study earlier than their planned end of study will have missing data imputed for the period of time between withdrawal from the study to the planned end of study visit first assuming missing at random (MAR) and then multiplying the estimated exacerbation rate under MAR by different deltas. The imputed exacerbation rates will vary independently for FF/UMEC/VI arms and FF/VI arms.

The deltas to be investigated are pre-selected multiples of the observed rate reduction. If the observed rate reduction from the key secondary analysis is  $x$ , the deltas to be investigated will range from  $1-x$  to  $1+3x$  for both active and placebo arms, in increments of  $0.5x$  (For example, if the observed rate reduction is 20% ( $x=0.2$ ) the imputed rates will be multiplied by deltas of 0.8 to 1.6 in increments of 0.1). The increment or range may be refined based on the analysis results and the location of tipping point.

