### 11.3.2. Variable Duration

The duration of the treatment period is variable but will be a minimum of 24 weeks and a maximum of 52 weeks.

For participants with an EOS visit, the visit will be mapped to the windows as specified in Section 11.3.1.

For participants who are lost to follow up or withdraw from the study early, then their planned EOS visit will be:

- if randomized date is on or after the 27th August 2017 then a participant's planned EOS visit is week 24.
- if randomized date is on or between the 7th May 2017 and the 26th August 2017 then a participant's planned EOS visit is week 36
- if randomization date is on or prior to the 6th May 2017 then a participant's planned EOS is week 52

If a participant has a EW visit past their planned EOS visit as defined above, then their planned EOS date become the next scheduled clinic visit (i.e. if a participant has a planned EOS visit of week 24 with an EW visit at week 28, then their planned EOS visit will become week 36). Similarly, if a participant is reported as lost to follow up after attending their planned EOS visit, then their planned EOS visit will become the next scheduled clinic visit. Thus,

- If a participant has a planned EOS visit of week 24, attends this visit and then is subsequently lost to follow up (for example, at week 28 based on study conclusion date), then their planned EOS visit will become week 36).
- If a participant has a planned EOS visit of week 24, does not attend this visit, and is lost to follow up at a later time point (for example, week 25 based on study conclusion date), then their planned EOS visit will remain as week 24.

The study completion date will be set at 181 days (i.e. 25 weeks and 6 days) post the final participant's randomization date.

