
 
• A participant is considered to have completed the treatment period if the answer to the question “Was the study treatment stopped permanently before the scheduled end of the treatment period?” on the Study Treatment Discontinuation eCRF page is “No”. Date of completion of treatment period will be the treatment stop date.
 
• A participant is considered to have completed the study if the answer to the question “Was the participant withdrawn from the study?” on the Study Conclusion eCRF page is “No”. Otherwise, if the answer is “Yes” then the participant is considered to have withdrawn early from study. The date of study completion/withdrawal as entered on the eCRF will be used as the study completion/withdrawal date.
 
• If a participant prematurely discontinues IP, according to the CRF instructions participants should be reported as continuing in the study if they attend either normal visits, or the safety follow-up visit after the early withdrawal visit (DSCONT=‘Y’). To identify participants who are continuing in the study per the normal visit schedule and providing post-treatment data, the following will be implemented:                             
 
○ If a participant prematurely discontinues IP and study at the same time, they are not considered to be continuing in the study (i.e. DSCONT will be “N”).
 
○ If a participant prematurely discontinues IP and only has an EW visit and a safety follow up visit on or after the date of IP discontinuation they are not considered to be continuing in the study (DSCONT will be “Y”). Note, if a participant initially continues in the study following IP discontinuation but then discontinues study prior to the next scheduled clinic visit they will be considered as not continuing in the study as they will not be providing post-treatment data.
 
○ If a participant prematurely discontinues IP and has a scheduled visit (not EW or safety follow-up visit) on or after the date of IP discontinuation then the participant is continuing in the study (DSCONT will be “Y”).
 
 
 

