On- and post-	1-52	- Up to EOS/ EW/study conclusion date*/date of death

Asthma Exacerbations		
treatment	1-24	
 
- If participants planned EOS visit is week 24: EOS/EW visit/study conclusion date*/date of death
 
- If participants planned EOS visit is later than week 24 use data up to the minimum of study day 169, EW, lost to follow up*, date of death.
 

	25-52	
 
- If participants planned EOS visit is later than week 24 and they have not withdrawn from the study before study day 170, then data from day 170 to EW/EOS /study conclusion date*/date of death will be included in the analysis.
 
- Data from participants who have withdrawn from study before study day 170 or whose planned EOS visit was week 24 will be excluded from these summaries.
 

On- and post-treatment sensitivity analysis	1-52	
 
- For participants with an EOS visit, all data up to the EOS visit will be included
 
- For participants without an EOS visit, all data available plus imputed data up to the participants planned EOS visit will be included.
 

On-treatment	1-52	
 
- If a participant does not withdraw from treatment prior to withdrawing from/completing the study (or being lost to follow up or dying) then up to last treatment date.
 
- If a participant withdraws from treatment prior to withdrawing/completing the study (or being lost to follow up or dying) then up to last treatment date+1
 

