	1-24	
 
- If a participant's planned EOS visit is week 24 and the participant does not withdraw from treatment prior to withdrawing from/completing the study (or being lost to follow up or dying): Last date of treatment
 
- If a participant's planned EOS visit is week 24 and the participant withdraws from treatment prior to withdrawing from/completing the study (or being lost to follow up or dying)): Last date of treatment +1
 
- If a participant's planned EOS is later than week 24 and participant does not withdraw from treatment prior to withdrawing from/completing the study (or being lost to follow up or dying): use the minimum of (169, Last treatment date)
 
- If a participant's planned EOS is later than week 24 and participant withdraws from treatment prior to withdrawing from/completing the study (or being lost to follow up or dying): use the minimum of (169, Last treatment date+1)
 

	25-52	
 
- If participants planned EOS visit is later than week 24 and they have not withdrawn from the treatment before study day 170 then data from day 170 up to the following timepoint will be used:                             
 
o If the participant does not withdraw from treatment
 
 
 

Asthma Exacerbations	
	
prior to withdrawing from/completing the study (or being lost to follow up or dying): Last date of treatment
 
 
○ If the participant withdraws from treatment prior to withdrawing from/completing the study (or being lost to follow up or dying): Last date of treatment+1
 
- Data from participants who have withdrawn from treatment before study day 170 or whose planned EOS visit was week 24 will be excluded from these summaries.
 

*if no study conclusion date, then use last contact date.	

 
• Denominators will be based on the number of participants with data available for the period being summarized.
 
• Exacerbations separated by less than 7 days will be treated as a continuation of the same exacerbation
 
• The duration of an exacerbation will be calculated as exacerbation resolution date or date of death - exacerbation onset date + 1.
 
	
Time to First Exacerbation	

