
 
• On- and Post-Treatment Exacerbations: The time to first exacerbation will be calculated as exacerbation onset date of first exacerbation – date of start of treatment+1. Participants will be represented from their Day 1 date to the start date of their first exacerbation up to and including the end of study date/early withdrawal date day. Participants that have not experienced an exacerbation on or before the end of study date/early withdrawal/ lost to follow up study/ date of death day are censored at the end of study date/early withdrawal date /study conclusion date (or date of last contact if no study conclusion date)/ date of death.
 
	

Asthma Control Questionnaire (ACQ)
General

Scoring instructions can be found Asthma Control Questionnaire: Background, Administration and Analysis, May, 2012.
 
The ACQ consists of seven attributes of asthma control (denoted as ACQ-7), and is to be administered on all scheduled clinic visits. Six attributes (ACQ-6), to be self-completed by the participant in a 6-item questionnaire, enquire about the frequency and/or severity of symptoms over the previous week in the following sequential order on: nocturnal awakening, symptoms on waking in the morning, activity limitation, shortness of breath, wheeze, and rescue medication use. ACQ-5 consists of the first five questions of ACQ, measuring asthma symptoms. The seventh attribute measures the lung function, which will be included via study visit spirometry assessment on pre-bronchodilator FEV1 % predicted value using Quanjer equation [Quanjer 2012]. The score for ACQ-5, ACQ-6, or ACQ-7 is the mean of the 5, 6 or 7 items, respectively.
 
 
• All 7 items of ACQ have response on 0-6 ordinal scale (0=no impairment/limitation, 6=total impairment/ limitation). For each version of ACQ (5, 6, 7), the total score is calculated as the
 

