On- and post-treatment	1-24	
 
- If participants planned EOS visit is week 24: EOS/EW visit/study conclusion date*/date of death
 
- If participants planned EOS visit is later than week 24 use data up to the minimum of study day 169, EW study conclusion date*, date of death.
 

	1-52	
 
- All health utilization data for participants with planned
 

	with $\geq 36$ planned exposure	EOS visit at Week 36 or Week 52.
*if no study conclusion date then use last contact date		

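### For subjects lost to follow-up with no EOS or EW visit, exacerbation time at risk runs to the eCRF study conclusion date, so any interval after the last observation would enter the rate analysis as near event-free time

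*SAP*

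**What the plan says.** Protocol 7.3.6 collects exacerbations from the start of randomised treatment to the EOS visit or, for subjects who leave the study, the EW visit. For subjects who have neither visit, the SAP sets the end date itself:

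- SAP 11.6.3, on- and post-treatment window for Weeks 1–52: "Up to EOS/ EW/study conclusion date*/date of death", with the footnote "if no study conclusion date, then use last contact date".
- SAP 11.6.3, time to first exacerbation: a lost subject without an event is censored at the "study conclusion date (or date of last contact if no study conclusion date" exists.
- SAP 11.6.3, healthcare use, for subjects planned beyond Week 24: "use data up to the minimum of study day 169, EW study conclusion date*, date of death", with the same footnote.
- SAP 11.6.1, on where the date comes from: "The date of study completion/withdrawal as entered on the eCRF will be used as the study completion/withdrawal date".

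For the model, SAP 7.2.5 states: "The logarithm of time (year) on study will be used as an offset variable". In the tipping-point analysis, data are "imputed for the period of time between withdrawal from the study to the planned end of study visit". Jump to reference likewise covers data missing after study withdrawal, and SAP 7.2.6 extends the offset only by the imputed time. SAP 11.7.2.2 starts imputation on the day after the EW visit and says nothing about subjects who have no such visit.

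**The concern.** The conclusion date and the last contact date are named as separate items, and the conclusion date takes precedence. Two places indicate that it can be the later of the two. Protocol 5.6.2 lets a site class a subject as lost only after repeated attempts at contact have failed. SAP 11.3.2 describes a subject planned for Week 24 who "attends this visit and then is subsequently lost to follow up (for example, at week 28 based on study conclusion date"; planned EOS then moves to Week 36. It also describes a subject who misses Week 24 and is lost at Week 25 by conclusion date, with planned EOS kept at Week 24.

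A moderate exacerbation needs the investigator's evaluation (Protocol 7.3.6.1). While a subject cannot be reached, an event can enter the data only if the site learns of it later, yet the time counts in the offset. SAP 7.2.5 intends data missing after early withdrawal to be treated as missing at random. A gap handled this way is treated instead as observed time with almost no events. Because imputation begins at withdrawal, neither imputation analysis would reveal it. The rate ratio concerned is tested at Levels 2 and 6 of the hierarchy, which gate the later tests.

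**Working it through.** **Step 1: the plan's own figure.** Inputs from Protocol 9.2.1–9.2.2: control rate 2.0/year, 20% reduction (1.6/year), dispersion k = 0.7, 750 per pooled arm, 39-week accrual.

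- Accrual: 52.5 + 112.5 + 157.5 + 202.5 + 247.5 + 315 + 1170 = 2257.5 subjects.
- The last subject reaches Week 24 at week 39 + 24 = 63. Entry by week 63 − 52 = 11 allows 52 weeks, and entry by week 63 − 36 = 27 allows 36. The shares planned for Weeks 24/36/52 are 47.8%/40.2%/12.0%.
- Mean planned follow-up: 0.478×24 + 0.402×36 + 0.120×52 ≈ 32.17 weeks (unrounded shares).
- Information per arm = n × E[μt/(1 + kμt)]. This gives SE(log rate ratio) = 0.0662.
- Power = Φ(|ln 0.8|/0.0662 − 1.96) = 0.921. The table in 9.2.2 gives 0.92. (The text of 9.2.1 says about 95%; without cutting follow-up to scheduled visits the result is 0.942.)

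**Step 2: size of a gap, closed form.** The documents give neither the share lost without an EOS or EW visit (f) nor the gap (g). Assumed: f = 1–10%, g = 2–12 weeks. The 10% is borrowed from the Week 24 missing-spirometry assumption in 9.2.1 and is not an upper limit. With lost subjects observed for half their planned time, T = 32.17(1 − f/2), and the apparent rate is the true rate × T/(T + fg).

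- f = 1%, g = 2: 32.01/32.03, a fall of 0.06%.
- f = 5%, g = 8: 31.37/31.77, a fall of 1.26%.
- f = 10%, g = 12: 30.56/31.76, a fall of 3.78%.

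**Step 3: the same under the planned model.** Negative binomial maximum likelihood, 600,000 simulated subjects per arm, last contact uniform over planned follow-up. The offset ends at last contact, or at last contact plus the gap.

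| Loss, triple/dual | Gap (weeks) | Arm rates | Rate ratio, to last contact → with gap | Shift in SE |
|---|---|---|---|---|
| 1%/1% | 2 | −0.08% | × 1.000 | – |
| 5%/5% | 4 | −0.77 to −0.81% | 0.8030 → 0.8033 | – |
| 5%/5% | 8 | −1.46 to −1.49% | 0.8030 → 0.8033 | – |
| 10%/10% | 12 | −4.09 to −4.17% | 0.8008 → 0.8015 | – |
| 6%/3% | 4 | – | 0.7974 → 0.7937 | −0.07 |
| 3%/6% | 4 | – | 0.8017 → 0.8058 | +0.08 |
| 6%/3% | 8 | – | 0.7996 → 0.7927 | −0.13 |
| 3%/6% | 8 | – | 0.7994 → 0.8070 | +0.14 |

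The falls exceed the closed form because the model gives short follow-up more weight per week.

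**Step 4: larger imbalance.** In 200 simulated trials of 750 per arm with an 8-week gap (planned follow-up 24/36/52 weeks in shares 55/33/12%), 5% triple/10% dual moves the ratio from 0.8021 to 0.8150, and the reverse moves it from 0.8020 to 0.7902. The first is ln(0.8150/0.8021)/0.0662 ≈ 0.24 SE. The closed form with 5% triple/10% dual and 12 weeks gives 0.800 → 0.816.

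**Step 5: the SAP's own examples.** In the Week 28 case, if Week 24 was the last observation, 36 − 24 = 12 weeks are unobserved. Of these, 28 − 24 = 4 count as observed and only 36 − 28 = 8 are imputed. In the Week 25 case the conclusion date is already past planned EOS, so nothing is imputed.

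**The case against.** The strongest reply is that no gap is shown. The eCRF completion guidelines are not among the documents. Protocol 5.6.2 governs when a subject is classed as lost, not which date is entered. An attended visit is not the last contact either: diary data are transmitted daily (Protocol 7.3.5), and unscheduled resupply visits are allowed. An event learned of later, with onset by the conclusion date, would count. All of this stands, so the point is conditional. A reader might infer that the plan demonstrably counts unobserved time as event-free; the documents show only that it can.

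From SAP 11.7.2.2 alone, a reader might also infer that the imputation start is undefined. It is not. SAP 7.2.5 starts at study withdrawal, and SAP 11.6.1, 6.1 and 11.4 supply a date for it. What remains is that 11.7.2.2 names only the EW visit and does not match 7.2.5.

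The on-treatment analysis ends at the last treatment date or the day after and uses time on treatment as its offset (SAP 7.2.6, 11.6.3), so it is unaffected. It answers a different estimand, which makes it a cross-check and not a correction.

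Finally, the conclusion-date rule is uniform across the SAP, and last contact is not defined there. Subjects are told to call when a diary alert fires (Protocol 7.3.5.1.6), so ending at last contact could tie the end of observation to events. That is a real cost, though a small one.

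**Conclusion.** Minor, and conditional on how sites complete the conclusion date. If they enter last contact, nothing changes. If they enter the date the subject was declared lost, arm rates are slightly understated over the assumed range. With equal loss the rate ratio is essentially unaffected. With a two-fold imbalance it moves by about 0.004–0.008 at 6% versus 3% and about 0.013 at 10% versus 5% with an 8-week gap, well within one standard error.

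A reader might infer a bias in favour of triple therapy, or a threat to Levels 2 and 6. The documents support neither: the direction depends on which arm loses more subjects, and no figure for that is given. The change is still worth making, because it alters nothing when the two dates agree and removes unobservable person-time when they do not.

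**What to change.** Before unblinding, and for the exacerbation and healthcare-use derivations in SAP 11.6.3 only:

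- When there is no EOS or EW visit, end the data window, the offset and the time-to-first censoring at the earlier of the study conclusion date and the recorded last contact date. Use the conclusion date if no last contact date is recorded. State what counts as last contact.
- Start tipping-point and jump-to-reference imputation on the day after that window ends, up to planned EOS. Where there is an EW visit, this remains the day after it. Put the same start date in 7.2.5, 11.6.3 and 11.7.2.2.
- List events with onset after the window that were learned of later.
- Leave the study phases in 11.4 and the disposition dates in 6.1 as they are.

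The cost is a minimum of two dates the SAP already names and one aligned sentence in three sections. A little person-time and any late-learned events leave the primary count. A last contact prompted by worsening asthma could raise the rates slightly. Exacerbations may also end on a different date from adverse events for these few subjects.

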**Asthma Control Questionnaire (ACQ)**

- average of all non-missing item responses [Asthma Control Questionnaire, Background, Administration and Analysis, May, 2012].
- Only one of the first five item responses are allowed to be missing in calculating the total scores for all versions of ACQ.
  - If the language of the ACQ conducted at a post-baseline visit is different to the language used at Day 1 baseline, all ACQ scores at that visit and all subsequent visits will be set to missing.
  - If the language of the ACQ changes during the run-in phase, stabilization phase and randomization, the change in these periods will only be calculated where the language remained consistent.
  - If the language of the ACQ is missing at any visit (including Baseline) and is the same at all remaining non-missing visits, the language at the missing visit will be assumed to be unchanged

